**Not applicable**

Questionnaires described above will be administered in a private setting at the Vermont Lung Center.

**Statistical Considerations:** *Delineate the precise outcomes to be measured and analyzed. Describe how these results will be measured and statistically analyzed. Delineate methods used to estimate the required number of subjects. Describe power calculations if the study involves comparisons. Perform this analysis on each of the primary and secondary objectives, if possible.*

**Analysis Plan.** Baseline comparability between the two randomized arms will be compared using demographic and outcome variables obtained at baseline to identify potential group comparison confounders. Primary outcomes assessed at the end of the study will be compared using a two-sample t-test and associated 95% confidence interval or a Kruskal-Wallis rank test and nonparametric confidence interval if distributional assumptions are of concern. This will be followed by a pre-post repeated measures mixed linear model to test for group specific baseline to follow-up differences, while for those measures observed at multiple time points, a linear mixed model incorporating time at discrete levels will be implemented. The previous t-test comparisons and the mixed models will be extended to covariance models using baseline mROS, age, sex, BMI, smoking history, duration of asthma and asthma medications, and a confounder score using all items. The effect of medications will be determined by using dummy variables for each class of medication, and by using the cumulative dose of inhaled corticosteroid and  $\beta$  agonist in the regression model. We will compare the rate of events describing any change in medications (whether an increase or decrease), including addition of new anti-asthma drugs and use of steroid tapers in the treatment and placebo groups. Missing data patterns from any lost to follow-up or incomplete data collection will be examined using standard approaches to assess missing at random or missing completely at random assumptions. If missing data is of concern, specific multiple imputation approaches for missing data will be implemented. Analyses using complete data and imputed data sets will be qualitatively compared and presented jointly.

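### Medication covariates, including cumulative corticosteroid and beta-agonist dose, are not limited to pre-randomisation values; if on-study dose is used, the adjusted MitoQ estimate may not be the total effect of assignment

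*Combined protocol and SAP*

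**What the plan says.** Under Statistical Considerations, the Analysis Plan begins with a check of baseline comparability "using demographic and outcome variables obtained at baseline to identify potential group comparison confounders". The first efficacy analysis is unadjusted: "Primary outcomes assessed at the end of the study will be compared using a two-sample t-test and associated 95% confidence interval", with a rank test as the alternative. A mixed model comes next: "This will be followed by a pre-post repeated measures mixed linear model to test for group specific baseline to follow-up differences".

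These analyses are then adjusted: "The previous t-test comparisons and the mixed models will be extended to covariance models using baseline mROS, age, sex, BMI". The list goes on to name "smoking history, duration of asthma and asthma medications", together with a confounder score built from all the items. The following sentence says how medication is handled: "The effect of medications will be determined by using dummy variables for each class of medication, and by using the cumulative dose". The drugs summed are inhaled corticosteroid and beta agonist, and their doses enter an otherwise unspecified regression model. No start or end of accumulation is given.

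The sentence after that treats medication as something that may differ by arm: "We will compare the rate of events describing any change in medications (whether an increase or decrease"). Other sections bear on the point:

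- Secondary outcomes lists rescue medication use from the daily diaries.
- Background Asthma Care allows add-on treatment as needed.
- Therapeutic Alternatives says that participants continue their usual asthma drugs.
- Randomization and blinding stratifies by centre.

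**The concern.** A covariate fixed before randomisation cannot be changed by treatment, so adjusting for it leaves the estimand alone. A dose accumulated after randomisation can be a consequence of treatment. If MitoQ improves asthma control, participants may use less rescue beta agonist. Holding that use constant then removes, or adds, part of what the trial is meant to measure.

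The text leaves room for this. Two analysts could fit different models from the same sentence, and only one of those models would keep to the total effect. Study Design says the pilot is to inform a decision on a full-scale trial. Readers of an adjusted estimate therefore need to know whether the adjustment dealt with chance imbalance or altered the effect itself.

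The named covariate list has a related gap. It omits centre, although randomisation is stratified by it. For the end-of-study models it also omits the baseline value of the outcome, which the pre-post mixed model already contains.

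**Working it through.** The plan gives no figure on this point, so there is none to reproduce. The check has two parts.

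**1. Which medication values are meant?**

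- *For on-study dose:* 'cumulative' implies accrual over a period. The sentence directly follows the one that puts asthma medications into the between-arm models, and directly precedes one on medication changes by arm. The visit schedule reviews concomitant medication through V5b, so on-study dose can be computed.
- *For baseline dose:* the section opens with variables obtained at baseline, and the word 'baseline' before mROS could be read as covering the whole list.
- *For a separate model:* the sentence is about the effect of medications, and could describe a model that is not the treatment comparison.

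No other section defines the period. Part of the Data Safety and Monitoring section was not available for this review.

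**2. What happens if on-study dose is used?**

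Notation, in SD units: G = arm (1 = MitoQ), M = on-study use, U = within-arm variation in use, Y = end-of-study outcome, δ = total effect.

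M = −d·G + U and Y = δ·G + r·U + e. Substituting U = M + d·G gives Y = (δ + d·r)·G + r·M + e.

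So the arm coefficient adjusted for M is δ + d·r, and the shift is d·r. It is downward if heavier use marks worse disease (r < 0) and upward if the drug itself improves the outcome (r > 0).

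The documents give neither d nor r. Assumed ranges are d = 0.25–0.5 and |r| = 0.3–0.6:

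- smallest shift: 0.25 × 0.3 = 0.075 SD
- largest shift: 0.5 × 0.6 = 0.30 SD

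Simulation with 400,000 draws and δ set to 0.667 (the shift does not depend on δ):

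| d | r | δ + d·r | simulated adjusted estimate |
|---|---|---|---|
| 0.5 | −0.6 | 0.367 | 0.366 |
| 0.5 | −0.3 | 0.517 | 0.518 |
| 0.25 | −0.3 | 0.592 | 0.590 |
| 0 | any | 0.667 | 0.664–0.669 |
| 0.25 | +0.3 | 0.742 | 0.743 |
| 0.5 | +0.6 | 0.967 | 0.968 |

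The unadjusted estimate stayed at 0.663–0.671 throughout.

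*Scale against sampling error.* The Sample size section plans 40 participants and 10% drop-out, so 40 × 0.9 / 2 = 18 per arm. The unadjusted SE is SD × √(2/18) = 0.333 SD. The shift is then 0.075/0.333 = 0.23 to 0.30/0.333 = 0.90 of that SE.

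*Mixed model.* A complete pre-post random-intercept model was simulated with n = 6,000, intraclass correlation 0.5, d = 0.5 and r = −0.45. Group-by-time contrast:

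| How dose enters | association arises at follow-up | association through stable severity |
|---|---|---|
| not at all | 0.674 | 0.693 |
| person-level main effect | 0.674 | 0.693 |
| dose × time | 0.458 | 0.704 |
| zero at V2, then accrued | 0.454 | 0.569 |

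A person-level main effect is constant over time and drops out of the within-person contrast. A dose accrued from randomisation and entered by visit is time-varying, because it is zero at V2. Only a negative r was run here; by the formula above, a positive r would move the follow-up case the other way.

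**The case against.** The strongest reply is that harm needs four things together: an on-study window, a model shared with arm, an effect of MitoQ on use, and a relation of use to outcome within arm. The documents establish none of them. The other items on the covariate list are baseline characteristics, and participants stay on their usual drugs. The first-listed analysis is unadjusted. The plan also compares medication changes by arm and treats rescue use as an outcome, so a reader would see whether use differed.

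Much of this stands. The concern is conditional, and it is confined to follow-on adjusted models. But the benign readings are not stated in the plan, and continuing usual controllers does not restrict rescue use. A by-arm comparison would show that use differed, but not how much of the gap between adjusted and unadjusted estimates came from it.

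Three stronger inferences are not supported:

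- *That the main comparison is biased.* The t-test or rank test contains no medication term.
- *That the shift can be put in mg/ml using the 3.0 in the Sample size section.* That figure is labelled within-person, not an end-of-study between-person SD. The methacholine series listed under Drug(s) stops at 4 mg/mL, and an SD of 3.0 or more would need values above that.
- *That the long covariate list must cost much precision.* That assumes every item enters separately. The plan also offers a single confounder score, which would largely avoid the cost. A score built from on-study dose would, however, carry the same shift.

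**Conclusion.** The concern holds in conditional form. The plan does not limit its medication covariates to values fixed before randomisation, and on-study dose is the likely reading. If that reading is followed, MitoQ changes use, and use is related to outcome within arm, the adjusted end-of-study estimate is not the total effect of assignment. The same can hold for a mixed-model contrast with time-varying or time-interacting dose.

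The illustrated size is less than one standard error. It rests on assumed d and r and on a linear model, so neither size nor direction can be fixed from the documents. The complete pre-post group-by-time contrast with dose only as a person-level main effect is untouched, as is the unadjusted comparison. A reader might infer that any adjustment for on-study dose is necessarily biased; that goes too far, because the shift vanishes if either d or r is zero.

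The omission of centre and of the baseline outcome from the named list is a plain fact of the text; its effect was not quantified.

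**What to change.** Amend the Analysis Plan as follows.

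1. State the time window of every medication covariate.
2. In all treatment-effect models, and in the confounder score, use only covariates fixed before randomisation. Take medication from the V1 and V2 record and from the run-in diary returned at V2.
3. Add centre to these models, and the baseline outcome to the end-of-study models.
4. Keep on-study cumulative dose and post-baseline drug-class indicators out of them.
5. Analyse on-study rescue use and medication changes as outcomes by arm, as Secondary outcomes and the Analysis Plan already intend.
6. Report any model of medication effects separately, labelled exploratory and not as the MitoQ effect.

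The cost is wording and slightly more reporting. No new data are needed, because medication review and diary cards are already collected by V2, where randomisation takes place. There are two downsides. The MitoQ estimate will include any effect that acts through changed medication use, and the report should say so. The run-in diary dose may also be incomplete, since exclusion criterion 19 admits participants with up to half of their diary days missing; the plan should say how such gaps are handled.

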### **Background Asthma Care**

Participants will be treated in accordance with asthma guidelines and best practices using materials already developed at our centers. All participants will be prescribed controller medication that includes inhaled corticosteroids and additional add-on treatments as needed.

**Rationale for study duration:** We based the duration of the study on the likely time needed to improve asthma control, and to determine the tolerability of the supplement over several weeks.

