### **Randomization and blinding:**

Treatment assignments will be stratified by center and the allocation ratio will be (1:1). Randomization will be accomplished by reviewing and confirming eligibility data; after verification of eligibility, a treatment assignment number corresponding to a unique study kit will be assigned. Study kits will be labeled with two-part tear-off labels with unique identifiers. The tear-off label will be affixed to a study form when the kit is assigned to a participant and the information will be keyed into data system to verify that assigned treatment was given to the participant.

**Procedures:** Describe all procedures (sequentially) to which human participants will be subjected. Identify all procedures that are considered experimental and/or procedures performed exclusively for research purposes. Describe the types, frequency and duration of tests, study visits, interviews, questionnaires, etc. Include required screening procedures performed before enrollment and while on study. Please provide in table, list or outline format for ease of review. (describe and attach all instruments)

Note: A clinical research protocol may involve interventions that are strictly experimental or it may involve some aspect of research (e.g., randomization among standard treatments for collection and analysis of routine clinical data for research purposes). It is important for this section to distinguish between interventions that are experimental and/or carried out for research purposes versus those procedures that are considered standard therapy. In addition, routine procedures performed solely for research purposes (e.g., additional diagnostic/follow-up tests) should be identified.

All procedures will be performed exclusively for research purposes.

Due to COVID-19 some of these procedures may not occur until guidelines allow it.

COVID testing and other precautions will be conducted according to current institutional guidelines.

Outline of Study Visits							
Week	-2	0 +/- 3 days	3 days after V2 +3 days	2 +/- 3 days	6 +/- 10 days	1-10 days prior to V5b	12 +/- 10 days
Visit number	V1	V2	Phone call ∞	V3 ∞	V4 ∞	V5a ∞	V5b ∞
Consent	*						
Baseline/interim history	*	*	*	*	*	*	*
Concomitant medication review	*	*		*	*	*	*
Collect and review diary cards		*		*	*		*
Treatment assignment (randomization)		*					
Drug distribution		*			*		
Drug titration			*				

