**Not Applicable**

Participants will stay on their usual asthma medications per their asthma care provider. There are no medications specifically targeting obese patients with asthma. The alternative is not to participate in this study.

***Data Safety and Monitoring:*** The specific design of a Data and Safety Monitoring Plan (DSMP) for a protocol may vary extensively depending on the potential risks, size, and complexity of the research study. For a minimal risk study, a DSMP could be as simple as a description of the Principal Investigator's plan for monitoring the data and performance of safety reviews or it could be as complex as the initiation of an external, independent Data Safety and Monitoring Board (DSMB). The UVM/UVM Medical Center process for review of adverse events should be included in the DSMP.

The DSMB will include 3 physician scientists (not from the University of Vermont or Duke University) who are active in asthma research.

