**Inclusion criteria:**

1. participant reported physician diagnosis of asthma
2. participant reported on regular prescribed controller therapy for at least 3 months
3. positive methacholine challenge (as determined by spirometry PD20 or oscillometry PD50 ≤ 4.0 mg/ml at visit 2)
4. age: ≥18 years
5. BMI ≥ 30 kg/m^2 (at visit 1)
6. poorly controlled asthma defined as one of the following:
  - a. Asthma Control Test Score ≤ 19 (at visit 1), or
  - b. Participant reported use of rescue inhaler on average > 2 uses/week for preceding month, or
  - c. Participant reported nocturnal asthma awakening on average 1 or more times / week in preceding month, or
  - d. Participant reported ED/hospital visit or prednisone course for asthma in past six months
7. ability and willingness to provide informed consent

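### The analysis plan promises an effect of background asthma medication that the design cannot estimate; the medication terms should be labelled as baseline adjustment only (minor)

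*Combined protocol and SAP*

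**What the plan says.** The Analysis Plan (Methods and Procedures, Statistical Considerations) first compares the arms at the end of the study with a two-sample test, then with mixed models. It extends both to covariance models using "baseline mROS, age, sex, BMI, smoking history, duration of asthma and asthma medications, and a confounder score using all items". The next sentence reads "The effect of medications will be determined by using dummy variables for each class of medication", and continues with a second route, "by using the cumulative dose of inhaled corticosteroid and" β agonist in the regression model. Nothing marks these terms as adjustment only, exploratory or non-causal, and no time window is given for the cumulative doses. The plan then compares, between the arms, the rate of any change in medication.

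Other sections say how these drugs are chosen. Background Asthma Care provides for "inhaled corticosteroids and additional add-on treatments as needed". Therapeutic Alternatives says "Participants will stay on their usual asthma medications per their asthma care provider". Under Randomization and blinding, only the study kit is assigned at random, 1:1 within center. One of the alternative definitions of poor control in the inclusion criteria is "Participant reported use of rescue inhaler on average > 2 uses/week for preceding month", and rescue use is also part of the diary measure of asthma control among the secondary outcomes.

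**The concern.** A drug class or dose chosen by need carries information about how bad the asthma is. If severity is left out of the model, the medication coefficient absorbs part of the effect of severity. This is confounding by indication, and it tends to make a drug look harmful. For rescue β agonist the problem is sharper. The trial's own definitions treat rescue use as a sign of poor control, so regressing airway reactivity on β-agonist dose partly regresses one marker of disease on another.

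The named covariates do not repair this. Methacholine response at baseline, FEV1, ACT score and exacerbation history are all absent from the list, and the confounder score appears to be built from the same list. What is at stake is a prespecified statement about background asthma drugs that could be published with the standing of a trial result although randomisation does not support it.

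**Working it through.** The plan gives no figure for a medication effect, so there is none to reproduce. The check has two parts: what the text allows, and how large the bias could be.

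**Text.** Three facts, taken together, give the confounding: medication is not randomised (Randomization and blinding); it follows need and the participant's own provider (Background Asthma Care; Therapeutic Alternatives); and no severity measure is named in the model (Analysis Plan).

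**Size, dose term.** From the documents: 40 participants and 10% drop-out (Sample size), so 40 × 0.9 = 36 completers. Everything else is assumed. Let S be severity, D dose and Y end-of-study methacholine response (higher is better), each with SD 1 before any treatment or medication effect is added. Let corr(D, S) = ρ and corr(Y, S) = -q, with true medication effect β = 0. A baseline response Y0 has the same relation to S as Y. Severity is stable, and the other covariates are independent of it. The mean coefficient of D, with S omitted, is then:

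- End-of-study model: -ρq.
- End-of-study model adjusted for Y0: -ρq(1 - q²)/(1 - ρ²q²).
- Change from baseline, Y - Y0: the S term cancels, giving 0.

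For ρ = q = 0.5, the first is -0.5 × 0.5 = -0.25 and the second is -0.25 × 0.75/0.9375 = -0.20.

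| Assumed ρ = q | End of study | Baseline-adjusted | Change from baseline |
|---|---|---|---|
| 0.3 | -0.09 | -0.08 | 0 |
| 0.5 | -0.25 | -0.20 | 0 |
| 0.6 | -0.36 | -0.26 | 0 |

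Simulated trials of 36, with arm and six other covariates in the model, agree with these values. In the end-of-study model a significant false harm appears in about 7%, 25% and 50% of trials, against a nominal 2.5% in that direction. In the change model the rate stays near 2.5%. With a true benefit of +0.1 SD, the end-of-study means are about +0.01, -0.15 and -0.26, while the change model recovers about +0.10.

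**Size, class dummy.** A second illustration uses 40 participants, with Y = -S + 0.5 × medication + 0.5 × arm + noise of SD 1. The log-odds of receiving the drug rise with S. All parameters are assumed.

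| Log-odds per SD of severity | Mean coefficient (truth +0.5) | Wrong sign | Mean coefficient with an error-prone baseline severity covariate |
|---|---|---|---|
| 0 | 0.50 | 13% | 0.49 |
| 0.5 | 0.03 | 48% | 0.25 |
| 1 | -0.31 | 76% | 0.05 |
| 2 | -0.71 | 96% | -0.24 |

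Adding a severity covariate reduces the bias but does not remove it. The coefficient of the randomised arm stays between 0.48 and 0.51 (truth 0.5) throughout, because in this set-up medication does not depend on arm.

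**The case against.** The best reply is that the sentence only specifies coding. It directly follows the sentence that lists asthma medications among the covariates, and the Objectives, Primary Outcome and Secondary outcomes contain no medication effect. This stands as a fair reading. It does not settle the matter, because the words still say that an effect will be obtained and carry no caveat. The text is ambiguous, and one sentence would resolve it.

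A second reply is that the primary outcome is a change and the plan includes a pre-post mixed model, in which stable severity cancels. That also stands, as the last column of the first table shows. It does not cover the end-of-study covariance model, a medication main effect in the mixed model, or need that varies during follow-up (step-ups, steroid tapers, rescue use).

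Third, the plan compares baseline outcome variables between arms to find confounders, and the score built from all items might be meant to include them. That step looks for imbalance between arms, not for the link between medication and severity, and the score most naturally refers to the items just listed.

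Fourth, the eligibility criteria narrow the range of severity, and baseline mROS may be related to severity. Both would tend to make the bias smaller than in the tables.

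A reader might also infer that the trial will report corticosteroid or β agonist as harmful. The documents do not support that: they do not say that the coefficients will be reported, and in the +0.1 SD case at correlations of 0.3 the mean estimate keeps the right sign.

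**Conclusion.** The point holds as a minor one. As worded, the plan promises a medication effect that this design cannot estimate without confounding by indication. The bias tends toward apparent harm, but its size and sign depend on the model and on correlations that the documents do not give. Over assumed correlations of 0.3 to 0.6 it runs from -0.09 to -0.36 SD per SD of dose in the end-of-study covariance model and from -0.08 to -0.26 with baseline adjustment. It is about zero for change from baseline if severity is stable.

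It would be wrong to conclude that the MitoQ result is compromised. The unadjusted randomised comparison does not use these terms. An adjusted MitoQ estimate could be affected only if the cumulative doses are accrued after randomisation, when MitoQ itself might alter them. The plan does not say whether they are, so this is a possibility to close off and not a demonstrated error.

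**What to change.** Replace the sentence on the effect of medications with:

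> Baseline medication class and baseline inhaled corticosteroid and β-agonist dose may enter the models as adjustment terms for the MitoQ comparison only; their coefficients will not be interpreted or reported as medication effects. On-study medication use and change will be compared by randomised arm and not used as covariates.

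The comparison of medication changes between arms that is already planned is kept. Restricting the terms to baseline also removes any adjustment for doses accrued after randomisation. Adding a severity covariate instead would not make the medication coefficients interpretable, as the second table shows.

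The cost is one sentence in the analysis plan, with no change to treatment, visits or data collection. The sponsor gives up a claim about background medication that the data cannot support.

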### Secondary outcomes

- ◆ Change in mitochondrial reactive oxygen species in nasal epithelial cells.
- ◆ Change in sputum, nasal lavage, serum and exhaled breath 8-isoprostanes.
- ◆ Change in induced sputum cell counts.
- ◆ Changes in asthma control documented with daily asthma diaries (including symptoms, rescue medication use, and peak flow measurements).
- ◆ Adherence monitored in daily asthma diary cards and by pill counts.
- ◆ The Asthma Control Test (ACT), a 4-week recall questionnaire that measures asthma control.
- ◆ The Marks Asthma Quality of Life Questionnaire (Marks AQLQ), an asthma-specific quality of life questionnaire.
- ◆ The Asthma Symptom Utility Index (ASUI), a 2-week utility-weighted asthma symptom questionnaire.
- ◆ Anthropometrics will include height and weight, and hip and waist measurements.
- ◆ Spirometry with bronchodilator will be performed to measure FEV1 and FVC in accordance with ATS/ERS standards.
- ◆ Forced oscillation (with methacholine testing) will be used to measure impedance, detect changes in the periphery of the lung.
- ◆ Adverse effects will be assessed by open-ended questions at each visit and rated in severity.
- ◆ Interval health history will be recorded at each clinic visit.
- ◆ Baseline questionnaires and exam will be administered to ascertain demographics, including self-reported ethnicity and race, general health, co-morbid conditions, asthma symptoms, and medication use.
- ◆ Exit questionnaires will be administered at the last visit to determine global assessments of treatment, adequacy of informed consent procedures, satisfaction with study procedures and personnel, and opinions about the intervention.

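### The medication-change comparison puts increases and decreases into one rate, so it has no direction and is diluted whenever step-downs also differ between arms

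*Combined protocol and SAP*

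**What the plan says.** The relevant sentence is in Statistical Considerations, Analysis Plan: "We will compare the rate of events describing any change in medications (whether an increase or decrease"). It describes one rate, and the parenthesis admits changes in both directions. The rest of the sentence brings newly added drugs and steroid tapers into that same rate. No other text available for review splits the comparison by direction or defines a step-up-only or net-change measure. Part of the Data Safety and Monitoring text was not available to check.

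Medication data have two other uses in the plan:

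- As model terms, in the sentence just before: "The effect of medications will be determined by using dummy variables for each class of medication", together with cumulative inhaled corticosteroid and beta agonist dose. These are covariates, not a comparison of arms by direction of change.
- As a diary outcome, under Secondary outcomes: "Changes in asthma control documented with daily asthma diaries (including symptoms, rescue medication use, and peak flow measurements"). This covers rescue use but not changes of controller, new drugs or steroid courses.

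Medication can change during follow-up. Background Asthma Care provides for "additional add-on treatments as needed", and the Therapeutic Alternatives section says: "Participants will stay on their usual asthma medications per their asthma care provider".

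**The concern.** An increase in controller dose, a new anti-asthma drug or a steroid course usually signals worse control. A decrease usually signals better control. An effective treatment would push the first group down and might push the second up. Adding them gives a number that measures how often medication changed, not whether participants did better or worse.

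Three readings of the result could then mislead. A small difference may hide a larger fall in step-ups. No difference may hide opposite shifts. An excess on active treatment may come from participants stepping down because they improved. The same weakness applies if the purpose is only to check that background treatment stayed balanced between arms, because opposite shifts are an imbalance that the pooled rate does not show.

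**Working it through.** **Plan's own figure.** There is none to reproduce. The documents give no rate, effect size or power for medication changes.

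**Inputs from the documents.** 40 participants (Sample size) and "the allocation ratio will be (1:1") (Randomization and blinding) give 20 per arm.

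**Inputs assumed.** All event rates below, in events per participant over follow-up, so that 30% is 0.30.

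**Formulas.** Let u be the step-up rate and d the step-down rate, with subscript 0 for placebo and 1 for MitoQ.

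- Pooled rate in each arm = u + d.
- Pooled difference = (u1 − u0) + (d1 − d0). It is zero only when d1 − d0 = −(u1 − u0). It changes sign when step-downs rise by more than step-ups fall.
- Pooled rate ratio = (u1 + d1) / (u0 + d0).
- Power: the sum, over all pairs of Poisson counts with means 20 × rate, of the probability of each pair for which the exact conditional (binomial, one half) test gives two-sided p ≤ 0.05.

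**Results.**

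| Assumed case | Placebo u + d | MitoQ u + d | Pooled ratio | Step-up ratio | Power, pooled | Power, step-ups |
|---|---|---|---|---|---|---|
| 1. Equal and opposite | 0.30 + 0.10 = 0.40 | 0.15 + 0.25 = 0.40 | 1.00 | 0.50 | 2.8% | 9% |
| 2. Partial offset | 0.30 + 0.10 = 0.40 | 0.15 + 0.20 = 0.35 | 0.88 | 0.50 | 3.2% | 9% |
| 3. Equal and opposite, larger | 0.40 + 0.10 = 0.50 | 0.10 + 0.40 = 0.50 | 1.00 | 0.25 | 2.9% | 36% |
| 4. Partial offset, larger | 0.40 + 0.05 = 0.45 | 0.10 + 0.20 = 0.30 | 0.67 | 0.25 | 7.6% | 36% |
| 5. Step-downs rare and equal | 0.40 + 0.05 = 0.45 | 0.10 + 0.05 = 0.15 | 0.33 | 0.25 | 31% | 36% |

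In case 2 a step-up difference of 0.30 − 0.15 = 0.15 appears as 0.40 − 0.35 = 0.05. In cases 1 and 3 the pooled test rejects only at its chance level, which is below 5% because the test is exact. If step-downs in case 2 were instead 0.30 on MitoQ, the pooled rates would be 0.40 against 0.15 + 0.30 = 0.45, an excess on active treatment although step-ups halved. In case 5 nothing is offset; equal step-downs only pull the ratio a little towards 1.

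**What a split can deliver.** For 0.30 against 0.15, expected step-up events are 20 × 0.30 = 6 and 20 × 0.15 = 3. The standard error of the log rate ratio is √(1/6 + 1/3) = 0.707. The 95% interval around 0.50 is 0.50 × exp(±1.96 × 0.707), about 0.13 to 2.00. Power is about 9%, or about 12% by Fisher's exact test on proportions. For step-downs, 0.10 against 0.25, the two figures are about 10% and 14%.

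**The case against.** The strongest case on the other side has four parts.

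- **Wording.** The sentence never says composite or net, and its parenthesis may only define which changes are recorded. It does not forbid a report by direction. This stands in part. But one rate is named, both directions are placed in it, and no split is planned, so a split chosen after the data are seen would be post hoc.
- **Purpose.** The sentence follows the covariate text and may be meant as a check on background treatment, not a measure of efficacy. That is a fair reading. It does not rescue the pooled rate, because in case 1 the arms differ twofold in step-ups while the check shows 40% against 40%.
- **Likelihood of step-downs.** Entrants have poorly controlled asthma, treatment lasts about 12 weeks, and participants stay on their usual medication under their own provider. Step-downs may be few, and case 5 may be closer to the truth. This stands, and it limits the size of the problem.
- **Stakes.** Medication change appears neither under Primary Outcome nor under Secondary outcomes, and separated comparisons have little power. This also stands.

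A reader might go further and infer that the plan will turn a true benefit into a null result, or that it has no interpretable information on worsening control. The documents do not support either. Exact cancellation needs equal and opposite shifts, and the documents give no rates that would make these likely. Control is also measured with a direction by the Asthma Control Test and the daily diaries, and the Asthma Symptom Utility Index is a listed secondary outcome (although the visit outline, as extracted, marks it only at visit 1).

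**Conclusion.** The point holds as a fault of definition in a supporting analysis. The planned rate mixes events of opposite meaning, so it cannot be read by itself as benefit, harm or balance of background treatment. The size depends on step-down rates that the documents do not give. Across the assumed cases it runs from a small loss (power 31% instead of 36% when step-downs are rare and equal), through dilution (a ratio of 0.25 becoming 0.67), to full cancellation when the shifts match.

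These figures rest on assumed rates, 20 per arm with no dropout, and Poisson counts with step-ups and step-downs independent. The primary comparison and the listed secondary outcomes are not affected. What the split gains is a result with a clear direction; it does not make the comparison well powered.

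**What to change.** In the Analysis Plan, replace the single comparison with two prespecified comparisons between arms:

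1. Escalation events: dose increase, new anti-asthma drug or systemic steroid course.
2. De-escalation events: dose decrease or withdrawal of an anti-asthma drug.

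Report each with a rate ratio and 95% confidence interval, and keep the pooled rate as a descriptive line only. State before unblinding how a steroid taper is counted (one course as one escalation event, with its planned reduction not counted again as a decrease) and how a return to a previous dose is classified. Label both comparisons as supporting. Do not make escalation the main measure of worsening control, since the Asthma Control Test, the Asthma Symptom Utility Index and the diaries are listed for that role.

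The cost is analysis wording and a coding rule. The visit outline already has concomitant medication review at every clinic visit, so no new data, visits or changes to participants' care are needed.
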